| Procedures (continued) | 
FOLFOX, patients whose scans show radiographic progression in the absence of clinical deterioration, including worsening ECOG PS, may remain on study treatments and an additional scan should be obtained 4 weeks (± 3 days) later as outlined in Section 8.1.1. If this subsequent scan shows disease progression, the patient will be discontinued from study treatments and followed for survival.
 
All on-study spiral CT/MRI scans for all patients enrolled on the study will be collected prospectively and submitted to a central imaging reader for archiving. These scans may be reviewed at a later time at the request of Lilly based on the criteria above.
 
End of Treatment (EOT) and Follow-Up Visits (30 days after EOT Visit):
 
All patients must have the EOT visit and Follow-Up visit 30 days after EOT visit with the procedures conducted as described in the protocol and schedule of events.
 
In this event-driven study, it is critically important for patients to continue to be followed for survival every 8 weeks for 12 months and every 12 weeks thereafter via record review and/or telephone contact.
 |
| Assessments of Safety | 
Safety and tolerability will be monitored through continuous reporting of adverse events (AEs) and serious adverse events (SAEs). Safety will be assessed by physical examination, standard clinical and laboratory tests (hematology, blood chemistry, and coagulations), and incidence of patients experiencing dose modifications, dose interruptions, and/or premature discontinuation of study drugs with reasons for study drug discontinuation. All AEs will be assessed for the relationship to study treatments, and the toxicity grade will be defined by National Cancer Institute Common Terminology Criteria for Adverse Events (NCI CTCAE) v4.03.
 |

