2.2.1 Treatment Duration

Each cycle is 14 days, with Days 6, 7, 13, and 14 being rest days for AM0010. FOLFOX will be administered on Day 1 of each cycle. Patients randomized to the investigational combination treatment (AM0010 plus FOLFOX) ARM 1, after completion of up to 12 cycles of combination chemotherapy or if experiencing chemotherapy intolerance (as defined as Grade 3 or 4 non-hematologic toxicity that has not resolved to baseline in 28 days or Grade 4 hematologic toxicity that has not resolved to baseline in 28 days) may continue to receive maintenance AM0010 if the patient continues to receive clinical benefit (CR, PR, or SD). Patients may receive FOLFOX on both study arms for up to 12 cycles or 24 weeks. Patients will be treated until tumor progression by RECIST v.1.1.

Patients may continue on treatment until they experience progressive disease, unacceptable toxicity, require palliative radiotherapy, withdraw consent, or their physician feels it is no longer in their best interest to continue on study treatments.

To mitigate the chance of detecting false-progression (ie, pseudoprogression) early in the course of treatment on ARM 1 with AM0010 in combination with FOLFOX, patients whose scans show radiographic progression in the absence of clinical deterioration including worsening ECOG PS as assessed by the Investigator may remain on study treatments and should have an additional scan 4

weeks (± 3 days) later as outlined in Section 8.1.1. If this subsequent scan shows disease progression, the patient will be discontinued from study treatments.

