4.2 Study Discontinuation

Patient study participation may be ended due to any of the following reasons:

- Withdrawal of consent
- Death
- Discontinuation of the study at the request of Lilly, a regulatory agency, or an IRB/IEC
- Loss to follow-up

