5.4 Supportive Care and Excluded Therapies

During the course of the clinical trial, patients are anticipated to continue the use of prescribed medications identified during the screening procedures, consistent with study inclusion and exclusion criteria.

The following therapies are not permitted at any point during the trial beginning with Cycle 1 Day 1 (if administered, the patient may be removed from the trial):

- Anti-cancer therapy, experimental or approved, other than FOLFOX and AM0010 administered in this study
- Immunomodulatory agents including, but not limited to, anti-CTLA4, anti-PD1, anti-PD-L1, sipuleucel-T, cyclosporine, and tacrolimus
- Coumadin
 - Patients on Coumadin should be changed to SQ administered LMWH or oral Factor II or Xa inhibitors with a $t_{1/2}$ of less than 24 hours
- Factor II or Xa inhibitor with a $t_{1/2}$ of greater than 24 hours
- High dose steroids (eg, dexamethasone ≥ 10 mg/day for more than 5 sequential days)
- Radiation therapy
- 5-FU must not be used or given in combination with brivudine, sorivudine, and analogues. An interval of at least 4 weeks between administration of fluorouracil and brivudine, sorivudine, or analogues should be kept.
- Cimetidine, metronidazole, and interferons during 5-FU treatment.
- Oxaliplatin has a known risk of Torsades de Pointes (TdP). Please refer to www.crediblemeds.org for a combined list of drugs that prolong QT and/or cause TdP.

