8.1.1 Pseudoprogression and Confirmation of Disease Progression

Accumulating evidence indicates a minority of patients treated with immunotherapy may derive clinical benefit despite initial evidence of PD. Patients treated with FOLFOX alone will not be permitted to continue their treatment beyond initial RECIST v1.1 defined PD.

Patients treated with AM0010 during the maintenance cycles in Arm 1 will be permitted to continue treatment beyond initial RECIST v1.1 defined PD if they meet the following criteria:

1. Investigator-assessed clinical benefit, and do not have rapid disease progression
2. Continue to meet all other study protocol eligibility criteria
3. Tolerance of study drug
4. Stable ECOG PS
5. Treatment beyond progression will not delay an imminent intervention to prevent serious complications of disease progression (eg, CNS metastases)

A radiographic assessment/scan should be performed 4 weeks (± 3 days) after original PD to determine whether there has been a decrease in tumor size, or continued PD. The assessment of clinical benefit should be balanced by clinical judgment as to whether the patients is clinically deteriorating and unlikely to receive any benefit from continued treatment with AM0010. A confirmatory scan will be required in the case of clinical deterioration suspected to be disease progression.

If the Investigator feels that the patient is deriving clinical benefit with continued treatment, the patients should remain on the trial and be monitored according to the SOE ([Appendix A](#)). The decision to continue treatment should be discussed with the Lilly Medical Monitor and documented in the study records.

For patients who continue AM0010 beyond initial progression, further progression is defined as an additional 10% increase in tumor burden volume from the time of initial PD. This includes an increase in the sum of all target lesions and/or the development of new measurable lesions. When assessing disease progression, the Investigator should use a new baseline tumor burden that includes new lesions that developed at the time of initial progression. Patients will discontinue study treatment upon confirmed PD (4 weeks after initial PD).

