- ^k Safety lab tests are listed. If Screening labs are done within 3 days prior, then Screening labs can be used as Day 1 labs. Laboratory tests performed as part of standard practice may be used for Screening if conducted within 21 days prior to Randomization.
- ^l Serum pregnancy test performed at Screening; urine pregnancy test performed locally at all other time points by dipstick as appropriate for women of child-bearing age. A urine sample for pregnancy testing for female patients will also be obtained at Day 1 of every odd-numbered cycle, every 28 days in patients who continue AM0010 monotherapy after FOLFOX discontinuation, EOT, and 30 days after EOT.
- ^m CA 19-9 (±3 days) will be evaluated at Screening, on Day 1 of every odd cycle, every 28 days after discontinuation of FOLFOX, and at EOT.
- ⁿ The collection of archived tumor tissues is not mandatory or required for eligibility. Attempts should be made to acquire these tissues starting once the patient is enrolled in the study. Pathology reports should be obtained.
- ^o Tumor response will be assessed by the study site and by an independent radiology reviewer. The process for collection of CT images for purpose of central independent review is described in the Imaging Manual. Patients whose scans show radiographic progression in the absence of clinical deterioration including worsening ECOG PS as assessed by the Investigator may remain on AM0010 plus FOLFOX study treatments and have an unscheduled scan, 4 weeks later as outlined in Section 8.1.1. If this subsequent scan shows disease progression, the patient will be discontinued from the study. Patients on subsequent scan and response (CR, PR, and SD) will remain on study treatments. Patients with CR or PR need to have a confirmatory scan (≥4 weeks). EOT scan done if not done within 4 weeks prior.
- ^p Randomization should occur within 21 days of starting baseline. Patients must begin treatment within 3 days after the date of Randomization.
- ^q Patients will be contacted via phone call to determine long-term survival status and record of any other anti-cancer therapy and cancer related surgery. The evaluation may be conducted by record review and/or telephone contact with the patient's treating physician.

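### Appendix A note o takes Arm 1 patients with confirmed progression off the study, where the rest of the plan stops only treatment; section 5.4 has a similar, permissive wording for both arms, so OS follow-up is put at risk

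*Protocol*

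**What the plan says.** **Confirmed progression.** Note o to the Schedule of Events (protocol Appendix A) covers patients whose scan shows radiographic progression without clinical deterioration. They "may remain on AM0010 plus FOLFOX study treatments and have an unscheduled scan" four weeks later. Then: "If this subsequent scan shows disease progression, the patient will be discontinued from the study".

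For the same event the protocol synopsis (Procedures) says: "If this subsequent scan shows disease progression, the patient will be discontinued from study treatments and followed for survival". Section 2.2.1 says: "If this subsequent scan shows disease progression, the patient will be discontinued from study treatments". Protocol section 6.4 stops study treatments and sends the patient to the end-of-treatment visit and survival follow-up. SAP section 6.4 also refers to study treatments only.

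**Leaving the study.** Section 4.2 begins "Patient study participation may be ended due to any of the following reasons" and names four: withdrawal of consent; death; discontinuation of the study by the sponsor, a regulator or an ethics committee; and loss to follow-up. Neither progression nor prohibited therapy is among them.

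**Prohibited therapy.** Section 5.4 lists treatments not permitted during the trial, including any other anti-cancer therapy, and adds: "if administered, the patient may be removed from the trial". Section 4.1 treats the start of new anti-neoplastic therapy before progression as a reason to stop study drug. Protocol section 6.6.2 records later anti-cancer therapy during survival follow-up, and SAP section 11.3.4 summarises it.

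**The concern.** The protocol keeps stopping treatment (section 4.1) apart from leaving the study (section 4.2), and the difference has practical effect. Under section 9.4.1, investigators need not actively seek adverse events once a patient has discontinued the study. Section 6.0 has all procedures performed as summarised in Appendix A, so the odd wording sits in the table that sites work from.

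The primary endpoint is OS, and SAP section 11.1 censors a living patient at the last contact before data cutoff. A patient taken off the study at confirmed progression would be censored at about that point. Progression is prognostic for death, so such censoring is informative. The note o pathway exists only in Arm 1, so it would act on one side of the comparison and tend to favour AM0010. The trial is open-label, so blinding would not even out how sites apply the two rules.

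**Working it through.** **1. The texts side by side**

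| Place | Event | Treatment | Participation / follow-up |
|---|---|---|---|
| Appendix A note o | Progression on repeat scan | – | Discontinued from the study |
| Synopsis, Procedures | Same | Stops | Followed for survival |
| Protocol 2.2.1 | Same | Stops | Not mentioned |
| Protocol 6.4 | Same | Stops | End-of-treatment visit, survival follow-up |
| SAP 6.4 | Same | Stops | Not mentioned |
| Protocol 4.2 | Reasons for exit | – | Progression not listed |
| Protocol 5.4 | Prohibited therapy | – | May be removed from the trial |
| Protocol 4.1 | New anti-neoplastic therapy before progression | May stop | Remaining study procedures continue |

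Note o is the only text that ends participation at confirmed progression. None of these texts keeps treatment going after that point, so the conflict concerns follow-up, not treatment.

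**2. Arms affected.** Note o names the combination. Section 8.1.1 says: "Patients treated with FOLFOX alone will not be permitted to continue their treatment beyond initial RECIST v1.1 defined PD". Arm 2 therefore never enters the repeat-scan pathway. Section 5.4 applies to both arms.

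**3. Design figures.** Inputs from protocol section 7.2: HR = 5.9/8 = 0.7375, two-sided alpha 0.05, power 85%, 1:1 allocation. With (1.960 + 1.036)² ≈ 8.98:

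- Schoenfeld: 4 × 8.98 / (ln 0.7375)² = 35.9 / 0.0927, giving 388 deaths.
- Freedman: 8.98 × (1.7375/0.2625)² = 8.98 × 43.8, giving 394 deaths.

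The stated 393 is reproduced. With looks at 276 deaths (0.015) and 393 deaths (0.045), power is 84.9% and total two-sided alpha 0.0496. Nothing here depends on note o.

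**4. Illustration of the risk.** The documents do not say how many patients a literal reading would remove, or how long they would live afterwards. These inputs are assumptions:

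- No true effect; 283 patients per arm; uniform accrual over 25 months; analysis at 393 observed deaths; 3,000 simulated trials per row.
- OS = time to progression + time from progression to death, both exponential. Every patient progresses before dying.
- Model A: medians of 3.0 and 2.0 months for the two parts (median OS 6.0). Model B: 2.0 and 3.2 months (median OS 6.2).
- A random share f of Arm 1 is censored 0.92 months (4 weeks) after first progression, if still alive.
- Unstratified log-rank test at |z| > 1.96; the last column counts results favouring AM0010.

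| f | Mean estimated HR, A / B | Arm 1 patients censored early, A / B | False finding for AM0010, A / B (nominal 2.5%) |
|---|---|---|---|
| 0% | 1.00 / 1.00 | 0 / 0 | 2.4% / 1.7% |
| 5% | 0.98 / 0.99 | 8 / 10 | 3.8% / 3.4% |
| 10% | 0.96 / 0.98 | 16 / 20 | 5.6% / 4.1% |
| 20% | 0.92 / 0.96 | 34 / 42 | 11.9% / 6.5% |
| 30% | 0.88 / 0.93 | 53 / 64 | 24.3% / 11.8% |

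The 0% row shows that the error rates are rough. The direction is the same in both models.

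**5. Power.** If deaths were lost and not replaced, fixed-design power at HR 0.7375 would fall from 85.5% (393 deaths) to 84.6% (10 lost), 83.7% (20), 81.6% (40) or 79.3% (60). The final analysis waits for at least 393 deaths, so the main effects would be delay and bias, not lost power.

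**The case against.** The strongest reply is that the plan as a whole keeps following these patients. The synopsis stresses survival follow-up as critical. Section 7.4.1.1 calls for it off treatment. Appendix A has its own survival-status row, with notes f and q, which do not exclude progressed patients. Section 6.6.2 describes the survival calls as taking place after the study, so leaving the study need not end contact. OS data would be lost only if a site put one footnote phrase above all of this. That stands, and it limits the point to a risk. It does not remove the contradiction, and it shows that note o departs from the sponsor's evident intent.

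Four stronger readings are tempting, and the documents do not support them:

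- **That section 5.4 requires removal, or removes one arm.** It is permissive and covers both arms. Sections 6.6.1 and 8.1 stop only imaging when new therapy starts. The SAP's OS sensitivity analysis that censors at subsequent therapy (section 11.3.5) presupposes that the primary analysis follows patients beyond it.
- **That later anti-cancer therapy is common here.** The one explicit rate given after second-line FOLFOX is 8%, from a cited randomised trial (section 1.1.1).
- **That the affected patients are close to death.** Note o selects patients without clinical deterioration. In the 21-patient Phase 1b cohort (section 1.3.2) median PFS was 2.6 and median OS 10.2 months; the gap is only indicative, but it does not suggest imminent death.
- **That the bias would be large.** If 10% of Arm 1 were lost at 12 weeks, all from the half with the shorter remaining survival, a true HR of 0.74 would appear as 0.67. That rests on an extreme prognosis assumption. With average prognosis in the same model there is no bias.

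The pathway's extent is also unclear. Section 8.1.1 restricts treatment beyond progression to maintenance cycles, while section 2.2.1 and note o describe it under the combination. Those passages need reconciling too; the number of patients exposed depends on it.

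**Conclusion.** The contradiction is real and is in the current text. Note o ends study participation at an event where the synopsis, protocol sections 2.2.1 and 6.4 and SAP section 6.4 end only treatment, and which section 4.2 does not recognise as a reason for exit. Section 5.4 has a milder form of the same ambiguity, in both arms. It is a wording inconsistency, not a fault of the design, and no planned figure changes.

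The consequence is a risk to the primary endpoint: literal use of note o would censor OS informatively in Arm 1 only, probably in favour of AM0010. The documents do not allow its size to be estimated. The illustrative HR of 0.96 to 0.98 at 10% of Arm 1 rests on an assumed share, assumed survival after progression, and loss at random among progressors. Because note o selects patients without clinical deterioration, the real bias could be smaller. The correction is still worthwhile: it costs almost nothing, and the alternative is a one-sided threat to the endpoint on which the trial is judged.

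**What to change.** - **Appendix A note o:** bring the last step into line with the synopsis, "the patient will be discontinued from study treatments and followed for survival".
- **Section 5.4:** state that receiving a prohibited therapy does not by itself end survival follow-up.
- **Both:** refer to section 4.2 as the only reasons for leaving the study, so that end of treatment, end of participation and survival follow-up are distinct.

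No treatment rule, sample size or analysis changes. The cost is a few words in a protocol amendment, or an administrative letter to sites.

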6.2.1.1.2 AM0010 plus FOLFOX: Cycles 1–12, Day 1 – Dosing

- Self-administer SQ Injection of AM0010; Dispense AM0010, and AM0010 Dosing Diary
- Administer FOLFOX every 14 days \pm 3 days (Section 5.1.2) for up to 12 cycles.
 - Patients will be treated with AM0010 administered SQ at the research clinic by a qualified staff member in the morning on Study Day 1. The Investigator or a qualified designee must be present during administration. Patients will be trained to self-administer AM0010 and will self-administer the dose daily throughout the study, starting with the first dose on Cycle 1, Day 1.

Note that if the patient is unable or unwilling to self-administer SQ injection of AM0010, the dose may be given by a caregiver.

6.2.1.1.3 AM0010 plus FOLFOX: Cycles 1, 2, and 4, Day 13

The following procedures and assessments will be conducted on Day 13 (\pm 3 days):

- Laboratory assessments (Day 13): CBC and differential with platelet count
- PK/ADA
 - Cycles 1 and 2, Day 13
 - Cycle 4 Day 13 Only
- Exploratory Biomarker Sample Cycle 1 Day 13, Cycle 2 Day 13, and Cycle 4 Day 13
- 12-lead ECG (Cycles 1, 2, and 4)

Note: In the event the clinical site business hours, weekends, or holiday schedule lead to missed PK/ADA time points, these time points will not need to be made up on a different day.

6.2.2 ARM 2: FOLFOX**6.2.2.1 FOLFOX Cycles 1–12: Day 1 (or up to 3 Days Prior) – Pre-Dose**

- Clinical evaluations:
 - Physical examination (modified physical examination at odd-numbered cycles capturing changes from prior examinations)
 - ECOG status
 - Weight
 - BSA calculation

- Vital signs (pulse, blood pressure, respiratory rate, and temperature)
- Concomitant medications
- Adverse events
- Patient-reported questionnaire (EORTC QLQ-C30 and EQ-5D-5L) – data to be collected on Day 1 of every treatment cycle regardless of dosing until 30 days after EOT
- ADA
 - Cycles 1 and 2, Day 1
 - Cycle 3 Day 1 Only
 - Cycle 5 Day 1 Only
- Exploratory Biomarker Cycle 1 Day 1
- Safety laboratory assessments (up to 3 days prior; if screening labs are done within 3 days prior then screening labs can be used as Day 1 labs):
 - Hematology
 - Serum chemistry
 - Urine pregnancy test (all females of childbearing potential – only on odd-numbered cycles)
- CA 19-9 on Day 1 of every odd cycle

Note: In the event the clinical site business hours, weekends, or holiday schedule lead to missed ADA time points, these time points will not need to be made up on a different day.

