6.2.2.2 FOLFOX Cycles 1–12: Day 1 – Dosing

- Administer FOLFOX every 14 days \pm 3 days for up to 12 cycles.

6.2.2.2.1 FOLFOX: Cycles 1, 2, and 4, Day 13

The following procedures and assessments will be conducted on Day 13 (\pm 3 days):

- ADA
 - Cycles 1 and 2, Day 13
 - Cycle 4, Day 13 Only
- Exploratory Biomarker Sample Cycle 1 Day 13, Cycle 2 Day 13, and Cycle 4 Day 13

Note: In the event the clinical site business hours, weekends, or holiday schedule lead to missed ADA time points, these time points will not need to be made up on a different day.

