7.6.3 Clinical Laboratory Data

Summary and change in laboratory data will be provided over time for hematology and chemistry parameters.

The NCI-CTCAE v4.03 grade for selected hematology parameters will be summarized by the most severe grade in each treatment cycle and the most severe grade during the study for each treatment arm. The number and percent of patients with NCI CTCAE v4.03 hematology value of Grade 3 or 4 that occur after the first dose of study drugs also will be presented. Shift tables may be provided.

Liver and renal function will be summarized using NCI-CTCAE v4.03 grade for selected chemistry parameters. The number and percent of patients with NCI CTCAE v4.03 chemistry values of Grade 3 or 4 that occur after the first dose of study drugs also will be presented. Shift tables may be provided.

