- ^r Staff administered dose and training for AM0010 self-injection on Cycle 1, Day 1. FOLFOX; Day 1 of each 14-day cycle for 12 cycles: *l-dl*-LV 400 mg/m² and oxaliplatin 85 mg/m² followed by bolus 5-FU 400 mg/m² and a 46- to 48-hour infusion of 5-FU 2400 mg/m².
- ^s Tumor evaluation by CT or MRI will be performed during Screening (within 4 weeks prior to Randomization), at Week 8 (±3 days) and every 8 weeks (±3 days) regardless of cycle number and regardless of any dose interruptions until PD by RECIST v.1.1. The same radiographic procedure used to define measurable or non-measurable lesions must be used throughout the study for each patient. The RECIST v.1.1 guideline recommends spiral CT images for chest, abdomen, and pelvis should be performed. Scans performed as part of standard practice may be used if conducted within 28 days prior to Randomization.
- ^t ARM 1: CBC and platelets only at Cycles 1, 2, and 4 Day 13.
- ^u If patient starts a new anti-cancer therapy within 30 days of the last dose of study medication, the Follow-Up visit should be performed prior to the start of the new anti-cancer therapy, within the 30-day window.

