7.2. Definitions and Conventions

The **date of randomization** is the date the patient was randomly assigned to pegilodecakin + FOLFOX arm or FOLFOX arm using the IVRS.

The **date of first dose** is the date of the first dose of pegilodecakin or any component of FOLFOX whichever is earliest.

The **baseline value assessment** for safety **in general** is the last value observed on or prior to the first dose of pegilodecakin or FOLFOX. For efficacy, the baseline value assessment is the last

value on or prior to the randomization date or the first value on or prior to the first dose of pegilodecakin or FOLFOX whichever occurs earlier.

The change from baseline will be calculated by subtracting the baseline values from the individual post-treatment values. If either the baseline or post-treatment value is missing, the change from baseline is set to missing.

The study day of a safety event or assessment will be calculated as:

- The difference between the date of the event or assessment and the date of first dose plus 1 for all events or assessments occurring on or after the day of first dose. For example, if an event occurs on 08 June 2014 and the date of first dose was 06 June 2014, the study day of the event is 3.
- The difference between the date of the event or assessment and the date of first dose for all events or assessments occurring before the day of first dose. For example, if an event occurs on 05 June 2014 and the date of first dose was 06 June 2014, the study day of the event is -1.

The study day of an efficacy event or assessment will be calculated as:

- the difference between the date of the event or assessment and the date of randomization plus 1 for all events or assessments occurring on or after the date of randomization
- the difference between the date of the event or assessment and the date of randomization for all events or assessments occurring before the date of randomization.

One month = 30.4375 days

One year = 365.25 days

Unless otherwise noted, summaries of continuous variables will include a mean, median, standard deviation, minimum, and maximum.

Unless otherwise noted, summaries of categorical variables will include the frequency and percentage (relative to the population being analyzed) of each category.

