Visit window approaches will not be used for this study. Visit based summaries will include scheduled assessments only. All scheduled and unscheduled post-baseline assessments will be used for derivation of minimum, maximum, and worst-case post-baseline values. All available data will be listed.

P-values will be rounded to 4 decimal places. P-values that round to 0.0000 will be presented as '<0.0001' and p-values that round to 1.000 will be presented as '>0.9999.' Confidence intervals (CIs) will be presented as 2-sided 95% CIs unless specified differently in specific analysis.

All data listings will present subjects in the ITT population, unless otherwise noted. For data listings, imputed dates will not be included and only the actual reported values will be displayed. As applicable, durations will be calculated and presented using imputed dates. When this occurs, a footnote will be added to the data listing indicating this.

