12.2. Clinical Laboratory Evaluations

Hematology and chemistry laboratory values will be graded according to CTCAE v4.03. These calculated grades will be summarized by cycle and maximum post-baseline grade over the entire study. Shift tables from baseline to worst post-baseline CTCAE grade will be generated.

A listing of abnormal laboratory events will be presented.

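### Three Day 13 blood counts are scheduled in Arm 1 only, and the worst-grade tables use every value, so part of any Arm 1 excess in cytopenia will reflect sampling

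*Protocol*

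**What the plan says.** Schedule of Events, note t to the Day 13 hematology entry: "ARM 1: CBC and platelets only at Cycles 1, 2, and 4 Day 13". Alone, that note could mean that only a CBC and platelets are drawn. The procedure sections settle it. Protocol 6.2.1.1.3 (Arm 1, Day 13 of Cycles 1, 2 and 4) lists "Laboratory assessments (Day 13): CBC and differential with platelet count". Protocol 6.2.2.2.1 (Arm 2, same days) lists antibody sampling and "Exploratory Biomarker Sample Cycle 1 Day 13, Cycle 2 Day 13, and Cycle 4 Day 13", with no blood count.

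Both arms have hematology before dosing on Day 1 of every FOLFOX cycle, at end of treatment (EOT) and at the 30-day follow-up. After FOLFOX stops, Arm 1 patients on maintenance have further counts every 28 days (Protocol 6.3.1 and 6.3.1.1). Arm 2 has nothing equivalent.

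On analysis, SAP 7.2 states: "All scheduled and unscheduled post-baseline assessments will be used for derivation of minimum, maximum, and worst-case post-baseline values". SAP 12.2 says of the laboratory grades: "These calculated grades will be summarized by cycle and maximum post-baseline grade over the entire study", and adds: "Shift tables from baseline to worst post-baseline CTCAE grade will be generated". Protocol 7.6.3 also plans "The number and percent of patients with NCI CTCAE v4.03 hematology value of Grade 3 or 4" occurring after first dose. The safety baseline "is the last value observed on or prior to the first dose of pegilodecakin or FOLFOX", so the Cycle 1 Day 1 pre-dose count is baseline. Neither document plans a worst-grade table limited to time points that both arms share.

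**The concern.** A worst grade is a maximum over looks, and a maximum can only rise as looks are added. Arm 1 has every scheduled FOLFOX-period count that Arm 2 has, plus three more. Two arms with identical true risk would therefore be expected to differ in these tables.

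The timing adds to this. In Arm 1, Day 13 is the day after the Day 12 injection, while the next Day 1 follows two rest days. Protocol 1.2.5.1.1 reports platelet recovery within 2-7 days of interrupting AM0010. A low Day 13 count may have recovered by the next Day 1, so it would be seen in Arm 1 and would have no scheduled chance of being seen in Arm 2.

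Comparing safety between arms is a stated secondary objective, and Protocol 1.3.2 names reversible thrombocytopenia as the most commonly reported adverse event. A reader of the planned tables could not tell how much of an Arm 1 excess is drug effect and how much is schedule.

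**Working it through.** The plan gives no figure on this point to reproduce, so the check is a count followed by a calculation under stated assumptions.

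**1. Scheduled post-baseline counts.** For a patient who starts C FOLFOX cycles with no maintenance:

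- Arm 2: (C − 1) Day 1 counts from Cycle 2 onward, plus EOT and follow-up, giving C + 1.
- Arm 1: the same, plus Day 13 of Cycles 1, 2 and 4, giving C + 4 once Cycle 4 is reached.

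This gives 8 v 5 at 4 cycles, 10 v 7 at 6 and 16 v 13 at 12. Six cycles is a reasonable middle case: the Phase 1b median PFS of 2.6 months (Protocol 1.3.2) is 2.6 × 30.4375 / 14 ≈ 5.7 cycles.

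**2. Within cycles.** For patients who go on to the next cycle, scheduled post-baseline counts are 1 v 0 in Cycle 1, 2 v 1 in Cycles 2 and 4, and 1 v 1 in Cycle 3 and Cycles 5-12. The by-cycle imbalance is confined to three cycles.

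**3. Effect on worst grade, equal true risk in both arms.** Let p be the chance that one count is Grade 3-4. The documents do not give p; 2%, 5% and 10% are assumed. With independent draws, the chance of at least one such value in k counts is 1 − (1 − p)^k. For example, at 6 cycles and p = 5%: 1 − 0.95^10 = 40.1% v 1 − 0.95^7 = 30.2%.

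Independence is unrealistic. The extra count is nominally two days before the next Day 1 count, and the windows (Day 13 ± 3 days; Day 1 labs up to 3 days early) overlap. A second calculation therefore used a latent normal variable with correlation r + (1 − r) × 0.5^(d/h) between counts d days apart, where r is the between-patient share and h a half-life in days. The assumed pairs (r, h) were (0.3, 3), (0.5, 3), (0.5, 7) and (0.7, 7), with 200,000 simulated patients each. At r = 0.5 and h = 3, counts two days apart have correlation 0.5 + 0.5 × 0.63 ≈ 0.81.

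Arm 1 v Arm 2, in percent, with the gap in points (taken before rounding):

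| Cycles | Counts | Independent, p = 2% | Independent, p = 5% | Independent, p = 10% | Correlated gap, all p |
|---|---|---|---|---|---|
| 4 | 8 v 5 | 14.9 v 9.6 (5.3) | 33.7 v 22.6 (11.0) | 57.0 v 41.0 (16.0) | 1.0-8.0 |
| 6 | 10 v 7 | 18.3 v 13.2 (5.1) | 40.1 v 30.2 (10.0) | 65.1 v 52.2 (13.0) | 0.7-5.6 |
| 12 | 16 v 13 | 27.6 v 23.1 (4.5) | 56.0 v 48.7 (7.3) | 81.5 v 74.6 (6.9) | 0.5-3.3 |

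The correlated gap is 0.5-8.0 points overall (Arm 1 to Arm 2 ratio 1.03-1.37). It is never negative, because the Arm 1 schedule contains every Arm 2 time point. Unscheduled values and maintenance visits are not in these figures.

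**4. With common time points only.** For patients without maintenance, counts become equal (7 v 7 at 6 cycles) and the schedule-only gap is zero.

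**The case against.** Several points on the other side stand.

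- **Size.** A reader might infer a spurious excess of up to 18 points by counting only to Cycle 5 Day 1 (7 v 4) and treating draws as independent: at p = 10%, 52.2% − 34.4% = 17.8. The documents do not support that reading. SAP 12.2 covers the whole study, and the extra counts are near-repeats of the Day 1 counts that follow them.
- **By-cycle tables.** They confine the problem to Cycles 1, 2 and 4. Visit-based summaries use scheduled assessments only, so Day 1 values can already be compared like for like. Neither is a worst-grade table over the study.
- **Status of the tables.** They are descriptive. No test of laboratory grades is stated and no efficacy endpoint uses them. Adverse event tables are less exposed, because Protocol 9.1.1 restricts which laboratory values are recorded as events.
- **Unscheduled counts.** Arm 2 is not limited to scheduled draws. Protocol 6.7.6 has local results behind a dose change or an adverse event assessment entered when central results do not support them. These could widen or narrow the gap.
- **Direction of the error.** Extra looks make AM0010 appear more toxic, not less. Making a Day 1 table the main comparison would sample Arm 1 after its rest days and could understate true toxicity. This is a good reason not to replace the all-values tables. It does not argue against adding a second set.

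**Conclusion.** The point holds for the descriptive by-arm hematology tables: maximum grade, shift, any Grade 3-4, and by-cycle for Cycles 1, 2 and 4. Following the plan as written raises Arm 1's observed worst grade through the schedule alone. The direction is certain for scheduled draws. The size is not in the documents; about 0.5-8 percentage points rests on assumed per-draw risks of 2-10%, equal risk in both arms, and the assumed time-decaying correlations. Arm 1 maintenance visits add looks beyond that.

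A reader might go further and infer that an Arm 1 excess in cytopenia would be an artifact. The documents do not support this. Day 13 directly follows AM0010 dosing, so part of any excess will be a real drug effect. What the planned worst-grade tables cannot do is separate the two.

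**What to change.** In SAP 12.2:

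1. Keep the all-values tables and footnote them: Arm 1 has three additional scheduled counts (Day 13 of Cycles 1, 2 and 4) and further maintenance counts.
2. Add hematology worst-grade and shift tables restricted to time points scheduled in both arms: Day 1 of FOLFOX Cycles 2-12, EOT and the 30-day follow-up. Exclude Arm 1 maintenance visits and any EOT or follow-up visit that comes after maintenance.
3. Present the two sets side by side whenever the arms are compared.

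The cost is one added table set from data already collected, with no change to visits or patient care. The common-visit tables omit some true Arm 1 nadirs, which the all-values tables still show. An Arm 1 patient who enters maintenance loses two visits that an Arm 2 patient keeps (for 12 cycles, 13 − 2 = 11 counts v 13). This small imbalance in the other direction should also be footnoted. Separately, note t (CBC and platelets) and section 6.2.1.1.3 (CBC with differential) describe the Day 13 count differently and should be reconciled.
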